- 3) If a sudden worsening of pain that does not occur in the normal progression of osteoarthritis occurs, the (sub) investigator will perform imaging test (X-ray and MRI) of the affected joint. Imaging test (X-ray and MRI) of other joints will be performed as needed by the (sub) investigator. Imaging tests will also be performed if the central adjudication office requests that additional tests be conducted. All images will be submitted to the central adjudication office.

3.3. Sample Size and Power Considerations

The original target sample size is 568 treated subjects (142 subjects per group)
(MT-5547 1 mg q4w group: 142 subjects; MT-5547 3 mg q4w group: 142 subjects; MT-5547 6 mg q8w group: 142 subjects; placebo group: 142 subjects)

After initiation of this study, based on the recommendations from the IDMC, the 3 mg q4w and 6 mg q8w groups were removed and 1 mg q8w group was newly added to the treatment groups.

The amended target sample size is 506 treated subjects, including the subjects who were randomized to 1 mg q4w/placebo groups before the amendment (approximately 40 subjects per group) and the subjects who are randomized to 1 mg q4w/1 mg q8w/placebo groups with the ratio of 1:1:1 after the amendment (142 subjects per group).

(MT-5547 1 mg q4w group: 182 subjects; MT-5547 1 mg q8w group: 142 subjects; placebo group: 182 subjects)

In addition, 57 patients each were enrolled in the MT-5547 3 mg q4w and 6 mg q8w groups prior to the protocol amendment (Ver. 04.00.00000) and were discontinued from study drug based on the recommendations from the IDMC. Thus, enrollment of 563 subjects is planned for this study in total.

The original rationale at the initiation of the study

Because this study is being conducted as a placebo-controlled study, in order to detect a statistical difference between the MT-5547 groups and the placebo group, the mean intergroup difference relative to placebo in both the change from baseline in the WOMAC pain subscale score and the change from baseline in the physical function subscale score at Week 16 for the MT-5547 3 mg SC q4w, 6 mg SC q8w, and 1 mg SC q4w groups was set at 1.1, and the standard deviation 2.5, on the basis of the results obtained in the overseas P2a study (R475-PN-0901) and the overseas P2b study (R475-PN-1227) (Table 3.3-1). The effect relative to placebo in the P3 study of 5 mg and 10 mg of tanezumab, another NGF inhibitor, was 0.81 to 1.21 in the WOMAC pain subscale score and 0.98 to 1.25^{24), 25)} in the WOMAC physical function subscale score, and it therefore appears that a mean difference between the MT-5547 groups and placebo of 1.1 is a realistic assumption. It also appears that the minimum clinically significant difference in each WOMAC score will be around 0.67 to 0.75^{26), 27)}. The aforementioned intergroup difference of 1.1 exceeds the minimum clinically significant difference, and therefore seems to be an appropriate value to use for the intergroup difference. Based on a one-sided significance level of 2.5% and multiplicity adjustment based on a gate keeping method using a graphical approach, the power for MT-5547 3 mg SC q4w, 6 mg SC q8w, and 1 mg SC q4w will be 90%, 88%, and 88%, respectively, for the primary endpoint, and 82%, 79%, and 79%, respectively, for the key secondary endpoint. A 2-sample t-test will be used for the tests in each step. Based on this assumption, the number of subjects who will complete 16 weeks of treatment in each group will be 120.

Furthermore, because the proportion of missing data for the primary endpoint and the key secondary endpoint at Week 16 is around 15% according to Table 3.3-1, it is being assumed that the proportion of missing data at Week 16 will be 15%, and the number of patients per group is therefore being set at 142.

The rationale after the changes in treatment groups

Assuming the absolute treatment difference of 1.1 between the MT-5547 1 mg SC q8w groups and placebo in both the change from baseline in the WOMAC pain subscale score and

the change from baseline in the physical function subscale score at Week 16 with an associated standard deviation of 2.5 based on the original rationale at the initiation of the study, the number of patients per group after the protocol amendment (Ver. 04.00.00000) is planned to 142 subjects per group. The structure of statistical hypotheses have been changed due to the removal of 3 mg q4w / 6 mg q8w groups and the addition of 1 mg q8w. It is noted that approximately 40 subjects per group were randomized to 1 mg q4w / placebo groups before the amendment. For evaluation on 1 mg q4w, since subjects are randomized to 1 mg q4w / placebo at the same time with the same ratio of 1:1 regardless of pre- or post- amendment, analyses will be performed with pooled comparable data including pre- and post- amendment data on 1 mg q4w / placebo (1 mg q4w group: 182 subjects; placebo group: 182 subjects). For evaluation on 1 mg q8w, analyses will be performed with only the post-amendment data (1 mg q4w group: 142 subjects; 1 mg q8w group: 142 subjects; placebo group: 142 subjects). For four null hypotheses, based on multiplicity adjustment based on a gate keeping method using a graphical approach (Figure 8.2.1-1 in section 8.2.1 of SAP for database at week 16), the power for MT-5547 1 mg SC q4w and 1 mg SC q8w will be 97% and 92% for the primary endpoint, 94% and 87% for the key secondary endpoint, respectively.

Table 3.1-1 Change From Baseline at Week 16 in the WOMAC Pain and Physical Function Subscale Scores

	REGN Study R475-PN-1227					REGN Study R475-PN-0901			
	Placebo (N=83)	MT-5547 1 mg (N=85)	MT-5547 3 mg (N=84)	MT-5547 6mg (N=85)	MT-5547 9 mg (N=84)	Placebo (N=55)	MT-5547 0.03 mg/kg (N=53)	MT-5547 0.1 mg/kg (N=53)	MT-5547 0.3 mg/kg (N=54)
Change from baseline in WOMAC pain subscale score									
Baseline	6.43	6.33	6.35	6.10	6.53	5.9	5.7	6.1	6.4
n ¹⁾	71	75	78	77	79	44	47	44	41
Mean ¹⁾ (SD) ¹⁾	-2.43 (2.38)	-3.49 (2.06)	-3.39 (2.44)	-3.07 (2.34)	-3.81 (2.49)	-2.4 (2.18)	-2.7 (1.89)	-3.4 (2.53)	-3.2 (2.24)
LSM ²⁾	-2.25	-3.35	-3.33	-3.03	-3.65	-	-	-	-
Diff. vs. Pbo ³⁾	-	-1.10	-1.08	-0.78	-1.40	-	-0.6	-1.1	-0.8
P value	-	0.0025	0.0029	0.0304	0.0001	-	0.1486	0.0090	0.0488
Change from baseline in WOMAC physical function subscale score									
Baseline	6.15	6.11	6.09	5.94	6.20	5.9	5.9	6.2	6.2

n ¹⁾	70	75	78	76	80	44	47	44	41
Mean ¹⁾ (SD) ¹⁾	-2.12 (2.26)	-3.21 (2.23)	-3.28 (2.29)	-2.97 (2.45)	-3.51 (2.50)	-2.3 (2.30)	-2.9 (1.78)	-3.4 (2.28)	-3.1 (2.18)
LSM ²⁾	-1.98	-3.08	-3.27	-3.03	-3.41	-	-	-	-
Diff. vs. Pbo ³⁾	-	-1.10	-1.29	-1.06	-1.43	-	-0.8	-1.1	-0.9
P value	-	0.0019	0.0003	0.0029	< 0.0001	-	0.0693	0.0071	0.0245

1) n: number of subjects at Week 16; mean: arithmetic mean at Week 16; SD: standard deviation at Week 16. However, in REGN Study R475-PN-1227, the n includes WOMAC data from after treatment discontinuation.

2) LSM: MMRM least squares mean

3) Diff. vs. Pbo: Difference for each group relative to the placebo group in the MMRM least squares mean

4. PLANNED ANALYSIS

4.1. Interim Analysis

A First-Step Analysis of the data was conducted using database in 24 week. No alpha adjustment is necessary, as the week 16 efficacy analysis is the final primary analysis for efficacy.

4.2. Final Analysis

This SAP for 68 week will be finalized before database lock in 68 week. The analysis for week 68 will be conducted after database lock in 68 week.

4.3. Independent Data Monitoring Board

An independent data monitoring board will periodically assess unblinded data, and will make recommendations to the study sponsor regarding the appropriateness of continuing the study and about the need for protocol amendments.

The independent data monitoring board will include independent statistical and medical experts. For more details, the overseas independent data monitoring committee procedures (DMC Charter) will be followed.

5. ANALYSIS POPULATIONS

The analysis of efficacy will be performed in the full analysis set (FAS). The principal analysis set for efficacy will be the modified FAS (mFAS). The analysis of safety will be performed in the safety analysis set (SAF). The analysis of pharmacokinetics will be performed in the pharmacokinetic analysis set.

The analysis sets are defined below. For the contents of the data review meeting, refer to a separate materials.

(1) Efficacy analysis sets

1) Randomized subjects (RAND)

2) FAS

The FAS will consist of all randomized subjects except for the following subjects.

- Subjects who have not received study drug even once
- Subjects with no WOMAC pain subscale score (the primary endpoint) at baseline
- Subjects with no WOMAC pain subscale score (the primary endpoint) at any time point after randomization

3) Modified FAS (mFAS)

The mFAS will consist of the FAS, except for the following subjects.

- Subjects who are randomized to 3 mg q4w group
- Subjects who are randomized to 6 mg q8w group

(2) SAF

The SAF will consist of all randomized subjects except for the following subjects

- Subjects who did not receive study drug even once
- Subjects for whom absolutely no post-randomization safety data are available

(3) Self-injection analysis set(SIAS)

The self-injection analysis set will consist of the mFAS, except for the following subjects.

- Subjects who never performed self-injection

(4) Pharmacokinetic analysis set (PK)

The pharmacokinetic analysis set will consist of subjects who have received investigational drug at least once and who had at least one non-missing post-dose serum drug concentration data.

(5) Anti-drug antibody (ADA) analysis set (ADA)

The ADA analysis set will consist of all treated subjects who received investigational drug or comparative drug at least once and who had at least one non-missing post-dose ADA result.

(6) Neutralizing anti-drug antibody (NAb) analysis set (NAb)

The NAb population includes all treated patients who received any amount of study treatment (drug or placebo; Safety Analysis Set), and either tested negative for ADA or tested positive for ADA with at least one non-missing NAb result (either "NAb negative" or "NAb positive") following the first dose of study drug or placebo.

(7) Concentration-Response analysis set (CR)

The CR population other than CRP will include all patients who received any study drug and who had at least one non-missing serum MT-5547 concentration following the first dose of study drug and at least one non-missing WOMAC pain subscale score, WOMAC physical function subscale score, alkaline phosphatase (ALP), or bone

specific alkaline phosphatase (BAP) value, as applicable for each C-R assessment. Placebo group patients who received any study treatment (i.e., placebo) and who had at least one non-missing WOMAC pain subscale score, WOMAC physical function subscale score, ALP or BAP value will also included as a reference for each C-R assessment other than CRP. For CRP, the CR population will include all patients who received any study drug and who had at least one non-missing serum MT-5547 concentration following the first dose of study drug and at least one non-missing CRP value which measured by Latex method. The data after the discontinuation will be excluded in CR population. For CRP, Placebo group patients who received any study treatment (i.e., placebo) and who had at least one non-missing CRP value which measured by Latex method will also included as a reference.

6. STATISTICAL CONSIDERATIONS

6.1. Descriptive Statistics

(1) Non-PK related

Continuous data will be summarized descriptively using the number in the analysis set (N), the number of observations (n), mean, standard deviation (SD), median, minimum and maximum. Categorical data will be summarized using frequency counts and percentages. The denominator for the percentages will be the total number of subjects in the treatment group and analysis population being presented, unless otherwise specified.

(2) PK related

Serum concentrations will be summarized descriptively using N, n, mean, SD, median, Q1, Q3, minimum and maximum by clinical study day (as defined in the protocol) and treatment group.

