Because this study is being conducted as a placebo-controlled study, in order to detect a statistical difference between the MT-5547 groups and the placebo group, the mean intergroup difference relative to placebo in both the change from baseline in the WOMAC pain subscale score and the change from baseline in the physical function subscale score at Week 16 for the MT-5547 3 mg SC q4w, 6 mg SC q8w, and 1 mg SC q4w groups was set at 1.1, and the standard deviation 2.5, on the basis of the results obtained in the overseas P2a study (R475-PN-0901) and the overseas P2b study (R475-PN-1227) (Table 3.3-1). The effect relative to placebo in the P3 study of 5 mg and 10 mg of tanezumab, another NGF inhibitor, was 0.81 to 1.21 in the WOMAC pain subscale score and 0.98 to 1.25^{24), 25)} in the WOMAC physical function subscale score, and it therefore appears that a mean difference between the MT-5547 groups and placebo of 1.1 is a realistic assumption. It also appears that the minimum clinically significant difference in each WOMAC score will be around 0.67 to 0.75^{26), 27)}. The aforementioned intergroup difference of 1.1 exceeds the minimum clinically significant difference, and therefore seems to be an appropriate value to use for the intergroup difference. Based on a one-sided significance level of 2.5% and multiplicity adjustment based on a gate keeping method using a graphical approach, the power for MT-5547 3 mg SC q4w, 6 mg SC q8w, and 1 mg SC q4w will be 90%, 88%, and 88%, respectively, for the primary endpoint, and 82%, 79%, and 79%, respectively, for the key secondary endpoint. A 2-sample t-test will be used for the tests in each step. Based on this assumption, the number of subjects who will complete 16 weeks of treatment in each group will be 120.

Furthermore, because the proportion of missing data for the primary endpoint and the key secondary endpoint at Week 16 is around 15% according to Table 3.3-1, it is being assumed that the proportion of missing data at Week 16 will be 15%, and the number of patients per

group is therefore being set at 142.

The rationale after the changes in treatment groups

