7.3. Data Handling Convention for Missing Data

(1) Non-PK related

Efficacy:

WOMAC

WOMAC scores will be computed when one pain, one stiffness, or 1-3 physical function items are missing. The missing items will be imputed by the mean of available items within the same subscale. The scores will be set to missing if more items are missing.

SF-36 / EQ-5D-5L

- SF-36 subscale scores will be computed if at least 50% of items are available. The missing items will be imputed by the mean of available items.
- EQ-5D-5L index will be set to missing if any of the 5 dimensions is missing.

Rescue Medication

If there is no date collected WOMAC, nominal date will be used.

Safety:

Adverse events

If severity or relationship is found to be missing the most severe occurrence will be imputed for the summary of interest.

For AE start missing or partial dates, the AE will be treated as TEAE if it cannot be determined to be a non-TEAE.

Laboratory test

Regarding hyaline casts and epithelial cells, set "Null" for blanks(= not detected) with date data.

Orthostatic Blood Pressure

If a retest is performed, the initial value should be compared with the retest value, and the value with the worst value should be used.

Other safety:

For safety summaries, only observed data will be used. If a value is indeterminate or a reference

value because of a problem with a test sample, then this value will be handled as a missing value.

(2) PK related

For PK summaries, only observed data will be used. Missing PK data will not be imputed. The PK data handling will be confirmed during blinded data review (BDR). PK data that are considered "invalid" will be flagged in the listing. Due to the nature of PK data, some issues may only be discovered after PK data are unblinded. Should new issues identified post unblinding, and new data handling rules would have to be applied, a separate PK data handling document will be produced to provide detailed rationale and decision making. If there is clear evidence that PK sample handling errors or other factors identified after data unblinding and these errors have led to unexpected erroneous data, then these erroneous data will be regarded as "invalid", full explanations will be given in the PK data handling document.

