8.3.4. ECGs

Absolute values and changes from baseline will be summarized at each assessment time point by treatment group for the following parameters.

- Heart Rate (bpm)

- PR (msec)
- RR (msec)
- QRS (msec)
- QT (msec)
- QTcF (msec)

The percentage of subjects with ECG values outside pre-defined limit will be summarized.

All data will be listed.

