8.3.9. Injection Site Assessments

Injection Site Assessments will be summarized at each assessment time point by treatment group. All data will be listed.

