8.3.11. Neurological Examinations

Neurological Examinations will be summarized by treatment group for the following tests.

- Cranial Nerve Exam
- Sensory Function
- Motor Function
- Reflexes
- Coordination

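### Week 68 SAP: the default whole-arm denominator is not overridden for by-visit categorical safety tables, so their percentages shrink by the fraction examined

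*SAP*

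**What the plan says.** Section 6.1 of both SAPs has the same sentence: "The denominator for the percentages will be the total number of subjects in the treatment group and analysis population being presented", followed by a clause that lets other sections specify otherwise. It has practical effect in the Week 68 SAP, where the relevant sections read as follows.

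- **Injection site (8.3.9):** "Injection Site Assessments will be summarized at each assessment time point by treatment group".
- **Neurological examination (8.3.11):** "Neurological Examinations will be summarized by treatment group for the following tests". The visits are listed in 9.3, and protocol 13.3.3 asks for proportions by group, time point and category.
- **Qualitative urinalysis (8.3.2):** listed among the parameters summarized at each time point.
- **Abnormal values:** for ECG (8.3.4), "The percentage of subjects with ECG values outside pre-defined limit will be summarized". Section 8.3.3 has a parallel sentence for vital signs. Neither states a visit or a denominator.
- **Missing data (7.3):** "For safety summaries, only observed data will be used".
- **Safety analysis set (section 5):** apart from untreated subjects, it removes only "Subjects for whom absolutely no post-randomization safety data are available".
- **Display rules:** a percentage of zero is left blank (9.1). The 3 mg q4w and 6 mg q8w arms are reporting columns (9.2). Section 9.3 marks follow-up (FU) week rows for several safety assessments, yet its footnote says follow-up visits are not shown in by-visit tables.

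The authors do set a different base where they want one. In 8.3.1, confirmed arthropathy is expressed among patients whose images required adjudication.

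**The concern.** In a by-visit table a finding can be recorded only in someone examined at that visit. Dividing by the whole arm mixes the prevalence of the finding with attendance. The printed figure falls as attendance falls, and two arms with the same prevalence but different attendance print different percentages.

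The Week 68 SAP plans no formal tests (6.2), so readers will judge these assessments from the descriptive tables. Neurological findings also feed one of the adverse events of special interest, altered peripheral sensation. In the two arms closed on the monitoring committee's recommendation, a row for a visit with no attendance should not look like a row of clean examinations.

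**Working it through.** **1. Does any section override the default?** Sections 8.3.2, 8.3.9 and 8.3.11 name no denominator. Section 7.3 restricts safety summaries to observed data, which rules out imputation but does not say what to divide by. The default therefore applies.

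**2. Formula.** With x abnormal among n examined in an arm of N:

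printed % = x/N = (x/n) × (n/N)

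**3. The plan's own planning figure.** Section 3.3 gives 120 completers per group and says that "it is being assumed that the proportion of missing data at Week 16 will be 15" percent. 120/0.85 = 141.2, rounded up to 142, which reproduces the planned 142 per group. The implied missing fraction is 1 − 120/142 = 22/142 = 15.5%. This is a rate for the WOMAC endpoints. Carrying it to safety examinations is an assumption made here for illustration.

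**4. Illustration (N = 142, n = 120, x = 12; the 12 is chosen for convenience).**

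| Category | Whole arm | Examined subjects |
|---|---|---|
| Abnormal | 12/142 = 8.5% | 12/120 = 10.0% |
| Normal | 108/142 = 76.1% | 108/120 = 90.0% |
| In no category | 22/142 = 15.5% | – |

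The abnormal figure is 1.5 points lower, or 15.5% lower in relative terms. The normal figure shrinks by the same factor, and the two categories together reach 120/142 = 84.5%.

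**5. Range.** Week 16 missingness in Table 3.3-1 (WOMAC pain) runs by arm from 5/84 = 6.0% to 13/54 = 24.1%. If safety examinations were missing at those rates, 10% among the examined would print as 10 × 0.940 = 9.4% down to 10 × 0.759 = 7.6%.

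**6. Closed arms.** Where nobody is examined, x/N = 0/N = 0, and 9.1 prints that as blank. Where subjects are examined and none is abnormal, x/N is again 0 and again blank. The abnormal row alone cannot tell the two apart; the normal row, if shown, can. On an examined-subject denominator the first case is 0/0, which is not estimable.

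**7. Vital-sign and ECG criteria (Appendix 2).** These fall into two kinds.
- Pulse, blood pressure, ECG heart rate and PR interval combine a threshold with a change from baseline. No baseline value can meet such a rule, so nobody is excluded by baseline status.
- QRS and absolute QTc require the baseline to be on the normal side of the threshold. Subjects already beyond it cannot enter the numerator but stay in a whole-arm denominator.

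Routine post-baseline ECG is scheduled only at Week 48 or discontinuation (protocol 9.2.4.1.4), and membership of the safety set needs only some post-randomization safety data. A subject can therefore count in the ECG denominator with no post-baseline ECG.

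**The case against.** The best defence is that section 7.3 confines safety summaries to observed data, which a programmer could take to mean observed subjects as the base. Counts are printed beside percentages, and a category sum below 100% signals the missing subjects. This stands in part: what the plan contains is an unresolved rule, and the dilution follows if 6.1 is applied literally. It does not dispose of the point, because 7.3 sets no denominator while 6.1 does.

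Several stronger readings are tempting, and the documents do not support them.

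- **That every percentage in both SAPs is affected.** The rule is a default. The Week 16 SAP's safety output consists of adverse event summaries only (2.2.2, 8.3.1), where the full safety set is the proper base.
- **That unexamined subjects are counted as normal.** They fall in no category. They read as normal only where the abnormal row stands alone.
- **That safety percentages are 15% too low at Week 16.** The 15% is a WOMAC planning figure. The vital-sign and ECG percentages are not stated as by-visit, discontinued subjects have these assessments scheduled at discontinuation, and no routine ECG falls at Week 16.
- **That unequal attendance would create a false contrast of about 11%.** That ratio comes from one pair of arms in study 0901: (47/53)/(44/55) = 0.887/0.800 = 1.11. The 1 mg arm against placebo in study 1227 gives (75/85)/(71/83) = 0.882/0.855 = 1.03, and the 0.3 mg/kg arm in 0901 reverses the direction: (41/54)/(44/55) = 0.759/0.800 = 0.95.
- **That the closed arms show zero by construction.** Protocol 8.3 keeps those subjects under observation after drug is stopped. A zero arises by construction only where nobody is examined, and it prints blank. The second visit-window table in 7.2 is redacted, so how their visits map to rows cannot be settled.

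**Conclusion.** The point holds for the by-visit injection-site, neurological and qualitative urinalysis tables of the Week 68 SAP. Applied as written, the default multiplies each percentage by examined/N. The size depends on attendance, for which the documents give no safety-examination figure. At the WOMAC planning rate it is about 15% in relative terms, or 1.5 points on a prevalence of 10%. A second, smaller gap is that no base is defined for the vital-sign and ECG abnormal-value percentages; the Week 16 illustration should not be carried over to them.

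Severity is minor. There are no formal tests. Arthropathy and joint replacement also have Kaplan-Meier analyses, with Cox models and patient-time rates for arthropathy. A change to a clinically significant neurological abnormality is also recorded as an adverse event (protocol 9.2.4.1.9), where the full safety set is the right denominator.

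**What to change.** Add to section 6.1 of the Week 68 SAP, in words such as these:

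> *For by-visit categorical safety tables the denominator is the number of subjects with a non-missing assessment at that visit. Both n and N are shown, and a row with n = 0 is marked not assessed. For vital-sign and ECG abnormal-value percentages the denominator is subjects with a baseline and at least one post-baseline value. For criteria that require the baseline not to meet the threshold (for example QRS and absolute QTc), subjects who met it at baseline are also excluded.*

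Keep the full safety set for adverse event incidence. Reconcile 9.3, which marks follow-up week rows and also says follow-up visits are not displayed. The Week 16 SAP needs no change on this point.

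The cost is small: a short text change and some table reprogramming, with no new data. Denominators will vary by visit, which is why n and N should both be printed. If the Week 68 database is already locked, protocol 13.4 requires the reason to be given and the results to be distinguished from those planned.
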